The following assessments will be administered as an interview and will be entered into REDCap by the interviewer at the end of the visit:

- 1) Concomitant Medications
- 2) Medical Event Form, if applicable
- 3) Health Changes Questionnaire
- 4) Time Since Last Cigarette Questionnaire

The following assessments will be completed by the participant directly in REDCap:

- 1) BDI
- 2) OASIS
- 3) COVID19 Symptom Questionnaire
- 4) Respiratory Symptom Questionnaire
- 5) MNWS
- 6) QSU (usual brand)
- 7) QSU (study cigarette)
- 8) Vaping Craving Questionnaire
- 9) CES (usual brand)
- 10) CES (study cigarette)
- 11) Vaping Evaluation Scale

- 12) PANAS
- 13) Cigarette Purchase Task - Usual Brand Cigarette Version (weeks 4, 8, 12 and 16 only)
- 14) Cigarette Purchase Task – Study Cigarette Version (weeks 4, 8, 12 and 16 only)
- 15) Cross-price Elasticity Task¹⁰⁹- e-cigarettes and combustible cigarettes (weeks 4, 8, 12 and 16 only) (for e-cigarette experimental conditions only)
- 16) Penn State Electronic Cigarette Dependence Index (weeks 8 and 16 only)
- 17) Respiratory Health Questionnaire (weeks 8 and 16 only)
- 18) FTND (weeks 8 and 16 only)
- 19) Perceived Health Risks Questionnaire (weeks 8 and 16 only)
- 20) Smoking Stages of Change Algorithm and Contemplation Ladder (weeks 8 and 16 only)
- 21) WISDM – Brief Scale
- 22) Snaith-Hamilton Pleasure Scale (SHAPS)
- 23) Drug Use Questionnaire – 1 month version (weeks 8 and 16 only)
- 24) Perceived Stress Scale (weeks 8 and 16 only)
- 25) Alcohol Use Questionnaire – 1 month version (weeks 8 and 16 only)
- 26) E-cigarette flavor rating questionnaire (weeks 4, 8, 12 and 16 only)

In the event that the REDCap website is not functioning, the assessments will be administered aloud and participant answers will be recorded securely. The interviewer will enter the data into REDCap when it resumes functioning properly. This information should be recorded in the 'End of Visit Evaluation Form'.

Biological Samples to be collected:

- 1) First void urine sample (Weeks 8 and 16 only)
- 2) Saliva sample (Weeks 8 and 16 only)

7.4. Interactive Voice Response System:

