After the week 16 visit, participants will be required to attend one additional visit the following day. During this visit, participants will have been encouraged to abstain from smoking until their next scheduled visit (approximately 24 hours later). The abstinence assessment session should be scheduled no less than 18 hours and no more than 30 hours after the Week 16 visit. Abstinence will be verified by an expired breath carbon monoxide level of less than or equal to 6 parts per million (ppm). This session will allow us to determine whether the experimental cigarettes and e-cigarette use (for the e-cigarette conditions) have reduced the effects of abstinence on these measures relative to the control conditions. If the participant does NOT meet abstinence criteria, he/she will only receive \$20 for the visit. Those who do meet abstinence criterion will do concurrent choice session

detailed below.

7.8.A Participants Who Meet Criteria for Abstinence

7.8.A.1 Measures/Assessments

Physiological measures collected and entered directly into REDCap by the interviewer at the end of the visit:

- 1) CO
- 2) Blood Pressure
- 3) Heart Rate
- 4) Body temperature
- 5) Oxygen saturation
- 6) Respiratory rate
- 7) Urine or Saliva Toxicology

The following assessments will be administered as an interview and will be entered directly into REDCap by the interviewer:

- 1) Concomitant Medications
- 2) Medical Event Form, if applicable
- 3) Health Changes Questionnaire
- 4) Time Since Last Cigarette Questionnaire

The following assessments will be completed by the participant directly in REDCap:

- 1) BDI
- 2) OASIS
- 3) COVID19 Symptom Questionnaire
- 4) Respiratory Symptom Questionnaire
- 5) MNWS
- 6) PANAS
- 7) QSU-brief - Usual Cigarette
- 8) QSU-brief - Study Cigarette
- 9) Vaping Craving Questionnaire
- 10) Cigarette Purchase Task - Usual Brand Cigarette Version
- 11) Cigarette Purchase Task - Study Cigarette Version
- 12) E-cigarette Purchase Task- E-cigarette Version
- 13) Snaith-Hamilton Pleasure Scale (SHAPS)

In the event that the REDCap website is not functioning, the assessments will be administered aloud and participant answers will be recorded securely. The interviewer will enter the data into REDCap when it resumes functioning properly. This information should be recorded in the 'End of Visit Evaluation Form'.

7.8.B. Participants Who Do Not Meet Criteria for Abstinence

7.8.B.1 Measures/Assessments

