9.1 Statistical Methods

Continuous outcomes will be summarized by mean, standard deviation, median and range. Categorical outcomes will be summarized by frequencies and percentages. Skewed continuous outcomes will be log- or square-root transformed as appropriate. Variables measured at each baseline visit will be averaged and the average will be used as the baseline measurement. As we expect conditions to be balanced on important baseline characteristics due to randomization, our primary analysis for all endpoints will not be adjusted for potential confounders. However, a secondary analysis will be completed for all outcomes adjusting for demographic characteristics (e.g., age), that we have found to be important in prior studies. Potential moderators (e.g., SSRI vs. non-SSRI antidepressant, depression vs. anxiety disorders, BMI above or below 30) will be explored by adding that term and the moderator-by-condition term to the model. We will examine age group and gender as potential moderators in a similar fashion.

Participants will be randomized in equal probability to one of the four conditions, with randomization stratified by site and menthol cigarette status. All analyses will follow the intent-to-treat principle (i.e. subjects will be analyzed according to condition assignment, regardless of compliance). The Primary Aim will examine the effects of condition on total CPD (study product and non-study product). CPD will be analyzed by week (mean over all days in a seven-day period) using a mixed model to account for repeated measures from the same individual.

Models will include baseline CPD as a covariate. Using a mixed model also allows us to include the effect of study site as a random effect. Additional analyses conducted using data collected at the end of the study will use orthogonal comparisons to test for a linear trend in the decrease in CPD, such that VLNCC + PF e-cig > VLNCC + TO e-cig > VLNCC > NNCC, with

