the largest reduction in the VLNCC + PF e-cig condition. As we expect that differences among conditions for some of the outcomes may not follow a linear pattern, we will use related planned comparisons to test for threshold effects, specifically contrasting the NNCC condition to all three VLNCC conditions, and NNCC to the two VLNCC + e-cigarette conditions.. Analysis of cigarette demand, smoke exposure and tobacco carcinogens (Aim 2) as well as additional outcomes, including subjective effects, will be analyzed in a similar manner. Because Exploratory Aim 3 is based on abstinence-induced effects and will be examined using data collected at a single visit at Week 17, analysis will be based on an analysis of co-variance model. In addition to the effect of condition, we will include important covariates noted above. Exploratory analyses will also be conducted combining data collected from three of the vulnerable populations (disadvantaged women of childbearing age, opioid dependent individuals, individuals with AD) to explore potential differences in effects of study condition across these populations. This will be done with the addition of the effects of population and population-by-condition terms to the models described above. Study staff will make every effort to minimize missing data, and results of our ongoing trial suggest that this will be minimal. We will examine the missing data pattern, and if it is missing at random, will use all data available, without imputation.

permutation tests.¹²¹

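### Section 9.1 analyses Aim 3 on the post-abstinence visit alone, which gives levels while abstinent but cannot support a statement that a condition reduced the effects of abstinence

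*Combined protocol and SAP*

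**What the plan says.** Three places describe Aim 3, and they do not ask the same question.

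- Section 1 (Objective) words it as exploring how the four conditions affect cigarette demand, craving and withdrawal while the abstinence assessment takes place. That is a comparison of levels.
- Section 7.8 gives the session a different purpose: "This session will allow us to determine whether the experimental cigarettes and e-cigarette use (for the e-cigarette conditions) have reduced the effects of abstinence", relative to the control conditions. That is a comparison of changes.
- Section 9.1 uses the language of change but the data of a level: "Because Exploratory Aim 3 is based on abstinence-induced effects and will be examined using data collected at a single visit at Week 17". The method it names for these data is ANCOVA.

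On covariates for Aim 3, Section 9.1 says only: "In addition to the effect of condition, we will include important covariates noted above". The candidates named earlier in that section are baseline CPD ("Models will include baseline CPD as a covariate") and, for secondary analyses, demographics ("a secondary analysis will be completed for all outcomes adjusting for demographic characteristics (e.g., age"). Baseline is defined by "Variables measured at each baseline visit will be averaged and the average will be used as the baseline measurement", so it precedes the 16-week experimental period. No Week 16 value, change score or condition-by-visit term is named for Aim 3.

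The pre-abstinence values are nevertheless collected. The even-week list in Section 7.3.A includes the MNWS, the QSU for usual and study cigarette, and both Cigarette Purchase Tasks, for example "Cigarette Purchase Task - Usual Brand Cigarette Version (weeks 4, 8, 12 and 16 only". Section 7.8 repeats these measures 18 to 30 hours after the Week 16 visit, for participants with a CO of 6 ppm or less.

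**The concern.** An effect of abstinence is the difference between a person's state while smoking as usual and that person's state after going without cigarettes. Whether a condition reduces that effect is a between-arm comparison of the difference. One post-abstinence measurement does not contain it.

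By the end of Week 16 the arms have used different products for 16 weeks. A difference that has arisen by then enters the next day's comparison in full. A baseline covariate cannot remove it, because it developed after baseline.

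An arm with lower demand or craving at Week 16 could therefore be credited with blunting abstinence even if its scores rose exactly as much as those of the control arm. Aim 3 is exploratory, so what is at stake is how its result is interpreted. The primary aim is not affected.

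**Working it through.** **Inputs from the documents.** 53 per condition, 15% loss, two-sided 0.05 and effect size 0.60 (Section 9.2); craving effect size 0.20 between normal and very low nicotine cigarettes (Table 2, Section 9.2).

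**Assumptions.** The Week 16 difference d persists unchanged to the session. Abstinence has the same effect in every arm. The correlations are assumed, because the documents give none.

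**1. The plan's own figure.** A two-sample t-test at d = 0.60 needs 45 evaluable per arm (power 80.4%), and 45 / (1 − 0.15) = 52.9, so 53. The stated sample size reproduces. It was set for Aim 1; no figure is given for Aim 3.

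**2. The session-only comparison when abstinence effects are equal.** The noncentrality is d / √(2/n).

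- n = 45: 0.20 / √(2/45) = 0.949, rejection probability 15.5%.
- n = 53: 0.20 / √(2/53) = 1.030, rejection probability 17.5%.

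If the result is read as an abstinence effect, these are false-positive rates against a nominal 5%.

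**3. Fewer participants.** Section 7.8.B gives those who fail the CO criterion no MNWS, QSU or purchase task, so 45 to 53 is an upper bound on the numbers. At an assumed 25 per arm the noncentrality is 0.20 / √(2/25) = 0.707 and the rejection probability 10.7%. The expected estimate is still 0.20 SD. Smaller numbers make the misreading less often significant, but no smaller.

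**4. What each form of analysis does.** Simulation with d = 0.20, 45 per arm and 4,000 runs per setting. Three settings were used for the correlation with baseline (r_b) and between Week 16 and the session (r_w): 0.3 and 0.5; 0.5 and 0.7; 0.6 and 0.8.

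| Analysis | Mean estimate (true abstinence effect 0) | Rejection |
|---|---|---|
| Session value only | −0.19 to −0.20 | 14–16% |
| Session value, adjusted for its baseline | −0.19 to −0.20 | 17–21% |
| Session value, adjusted for baseline and Week 16 | −0.06 to −0.11 | 8–10% |
| Change from Week 16 to session | about 0 | 5.2–5.4% |

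Baseline adjustment leaves the estimate where it was and only sharpens it. Week 16 used as a covariate removes part of the difference. The slope on Week 16 given baseline is (r_w − r_b²)/(1 − r_b²), which is 0.45, 0.60 and 0.69 in the three settings. The remainder is 0.20 × (1 − slope) = 0.11, 0.08 and 0.06. Of these four analyses, only the change contrast targets the quantity in Section 7.8.

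**5. Precision of the change.** With equal variances its SD is √(2(1 − r_w)) times that of the level: 0.77 at 0.7, 1.00 at 0.5, and larger than 1 below 0.5.

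**The case against.** The strongest reply is that Section 1 is where the aims are set, and its wording asks for levels under abstinence. For that question a single-visit ANCOVA is a suitable analysis, and the 15.5% to 17.5% above is power to detect a real condition difference. This stands. The rates become errors only when the result is reported in the terms of Sections 7.8 and 9.1.

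Three stronger readings are tempting, and the documents do not support them.

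- A reader might infer that the arms are expected to differ at Week 16 on all three Aim 3 outcomes. Section 1 hypothesises a Week 16 difference for cigarette demand only. Table 2 gives craving at 0.20, from earlier cigarette-only data with no e-cigarette arm. Nothing is given for withdrawal.
- A reader might put the false-positive rate near one half. That takes a carried-over difference of about 0.40 SD (46.7% at 45 per arm, 53.2% at 53), a value the documents do not give for any Aim 3 outcome.
- A reader might suppose that a change analysis loses only the few people without a Week 16 visit. It also lacks everyone who fails the CO criterion, as does the session-level analysis.

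It can also be said that change is not automatically the better measure: an arm that already has raised withdrawal at Week 16 has less room to rise. This too stands, and is a reason to report level and change together. Finally, Section 1 describes abstaining during a three-hour laboratory session and Section 7.8 about 24 hours beforehand; the passages should be reconciled so that the exposure being contrasted is clear.

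**Conclusion.** The concern holds as a mismatch between the stated purpose and the analysis. Sections 7.8 and 9.1 speak of effects of abstinence; the ANCOVA in 9.1 estimates levels while abstinent. Any Week 16 condition difference that persists is carried into the estimate in full. At 0.20 SD, with equal abstinence effects, that means significance in 15.5% to 17.5% of trials at 45 to 53 per arm, and less often with the smaller number of CO-verified abstainers. The size rests on the craving figure in Table 2 carrying over to this trial and on its persisting to the session. The direction of the argument needs neither assumption.

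It would go too far to call the Aim 3 analysis invalid: it answers the question in Section 1. Nor does a change contrast cure everything. Both analyses are made in participants selected after randomisation by meeting the CO criterion, and neither is a fully randomised comparison.

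**What to change.** In Section 9.1:

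- Add a Week 16 to abstinence-session contrast, as within-person change or as condition-by-visit in a mixed model, for the measures taken at both visits: MNWS, QSU (usual and study cigarette) and Cigarette Purchase Task (usual-brand and study versions). Base any statement about reduced effects of abstinence on this contrast.
- Keep the session ANCOVA as the analysis of Aim 3 as worded in Section 1, labelled as level during abstinence. Report the E-cigarette Purchase Task only in this way, because the Week 16 list does not contain it.
- Report the number of verified abstainers in each arm, and state that both analyses are in a subset selected after randomisation.
- Align the wording of Aim 3 across Sections 1, 7.8 and 9.1.

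The cost is a few sentences and slightly more analysis work, with no new visits, data or participants. The downside is precision: the change is noisier than the level if the Week 16 to session correlation is below 0.5.

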10.1 Risks of Participation

- 1) Survey Questionnaires. This interview will include questions about your medical and psychiatric histories, drug and alcohol use and history, breath tests for cigarette and alcohol use, urine or salivary tests of illicit drug use and pregnancy, and questionnaires about your mood. Answering these personal questions could make you uncomfortable. If you report thoughts of killing yourself or other indicators of suicidality, a study clinician will come to talk to you. You may also request to see a study clinician if you are in discomfort and would like help and/or referrals for mental health resources.
- 2) Breach of Confidentiality: The risk of the interview is loss of privacy if other people find out the results.
- 3) Undue Influence: Undue influence is a possible risk due to monetary compensation for participating in these studies. The likelihood of this risk is low because the compensation is commensurate with the amount of time and effort required for these studies.
- 4) Drug Testing: A breach of confidentiality could occur and other people could learn of the participant's drug use.
- 5) Obtaining Blood Pressure and Heart Rate. The blood pressure cuff may cause minimal discomfort. In obtaining blood pressure we may find a participant to have abnormal blood pressure and/or heart rate. If participant's blood pressure is abnormal, we will inform the participant of this, and participant may be advised to see a doctor, and may also be contacted by our study doctor. Also, smoking and nicotine can affect the cardiovascular system, which may result in changes in blood pressure and/or heart rate.
- 6) Smoking Cigarettes: All cigarettes are detrimental to a person's health and can lead to significant medical problems including:
 - a. Cardiovascular Diseases: Coronary heart disease, heart attack, stroke, peripheral vascular disease, reduced blood circulation, abdominal aortic aneurysm
 - b. Respiratory Diseases: Emphysema, bronchitis, and chronic airway obstruction
 - c. Cancers: Cancer of the lung, bladder, cervix, esophagus, kidney, larynx, mouth, pancreas, throat, and stomach; leukemia
 - d. Metabolic Diseases: Type 2 Diabetes
 - e. Other Health Risks Associated with Smoking: Including but not limited to infertility, lower bone density in postmenopausal women, and hip fracture in women

e. Death

- 7) **Smoking Study Cigarettes.** All cigarettes are harmful to a person's health and can lead to cardiovascular (heart) disease, respiratory (lung) disease, cancer and other health problems. In addition to the above medical problems, you may experience some minor negative health effects such as headaches. You may also experience smoking withdrawal symptoms, which are listed below. In addition, due to the altered nicotine levels, there could be a change in your use of cigarettes including the manner in which you inhale the smoke. Smoking the study cigarette does not necessarily provide any less risk than your usual brand of cigarette and could pose increased health risks.
- 8) **Using Study E-cigarettes.** E-cigarettes are devices that heat nicotine to produce an aerosol. The health effects of e-cigarettes are still unclear, but appear to be less than that for tobacco cigarettes. Most e-cigarette users have lower nicotine levels than when they smoked regular cigarettes. Some e-cigarette users, especially those who use both e-cigarettes and regular tobacco cigarettes as well as youth and young adults, can have increased nicotine levels. In some rare cases, these use patterns have been associated with seizures. Whether this would occur with the concurrent use of very low nicotine cigarettes is unclear. E-cigarettes users very often maintain addiction to nicotine, but this addiction appears to be somewhat less than that from tobacco cigarettes. Abruptly quitting e-cigarettes could cause withdrawal symptoms similar to those from quitting tobacco cigarettes (see below) but slightly less severe. The most common side effects include dry mouth, irritation of the throat and mouth, and mild cough. The JUUL and Vuse e-cigarettes we will be providing have not been well-studied but appear to be of similar risk to other e-cigarettes. You may have heard that e-cigarettes, or "vapes," can explode and seriously injure people. Although they appear rare, these explosions are dangerous. The exact causes of these incidents are not yet clear, but some evidence suggests that battery-related issues may lead to vape explosions. In order to prevent e-cigarette related injuries, keep your e-cig away from other metal objects, never charge your e-cig with a phone or tablet charger, don't charge your e-cig overnight or leave it charging unattended, and stop using the e-cig if the batteries get damaged or wet. Always keep e-cig liquid out of kids' and pets' reach and sight after use. If we learn about additional risks of e-cigarettes during the study, we will inform you of these risks.

Mood and Psychiatric Symptom Changes. You may experience smoking withdrawal symptoms during this study. These symptoms can include anger, anxiousness, craving for a cigarette, depressed mood, difficulty concentrating, frustration, increased appetite, impatience/impulsivity, irritability, restlessness, sleep problems, and weight gain. These feelings can be uncomfortable and can last a couple of weeks, but usually are of minimal risk. In addition, if you have a past history of anxiety, depression, or alcoholism, it is possible withdrawal could cause substantial increases in depression and anxiety symptoms, but this appears to be rare. At each visit, we will ask you how you feel. If you or we think that being in this study is putting your mental health at risk, we may have you meet with an on-site clinician and/or stop participating in the study. Further, if you report thoughts of killing yourself or other indicators of suicidality, a study clinician will come to talk to you. You may also request to see a study clinician if you are in discomfort and would like help and/or referrals for mental health resources.

- 9) **Returning to Regular Smoking:** It is possible that if participants return to smoking their usual brand of cigarette at the end of the study they may experience mild and transient

nausea, dizziness, and lightheadedness.

10) **Risk to Fetus.** To avoid risks to a fetus, it is important that you are not pregnant during this study. Avoiding sexual activity is the only certain method to prevent pregnancy. However, if you choose to be sexually active, you should be using approved forms of birth control if applicable determined by the Project Medical Director, including but not limited to prescribed birth control pills, patch, ring, injections, implants or intrauterine device (IUD) or an appropriate “double barrier” method. If you choose to be sexually active during this study, pregnancy could still result even with the use of these birth control methods.

10.2 Avoiding Risks to Fetus:

If participants choose to be sexually active, they should use an appropriate “double barrier” method of birth control (such as female use of a diaphragm, or contraceptive sponge, in addition to male use of a condom) or the female should be using prescribed “birth control” pills, patch, ring, injections, implants or intrauterine device (IUD) if applicable determined by the Project Medical Director. If a participant endorses a “double barrier” method, our medical professional will speak to the participant to confirm which methods will be used during the duration of the study. Participants will be tested for pregnancy every two weeks beginning at screening through the last study visit. If a participant becomes pregnant during the study, she will be withdrawn from the study. Approximately 30 days after being withdrawn or having a positive pregnancy test at the last study visit, the research staff will call the participant to confirm her due date. The licensed medical professional will follow-up with the participant after delivery to ask questions about the baby’s health.

10.3 Expected benefits of participation:

There are no benefits from participating in the study. The information obtained from this study may ultimately help the Food and Drug Administration decide how best to regulate nicotine and tobacco products with the goal of improving public health.

11. Protection Against Risk

